**Detailed Strategies for the Recruitment Plan.**

Efforts will be made by the applicant (PI), to implement a successful recruitment plan, and to avoid any source of coercion during the actual process. Twenty Veterans (10 in

intervention group vs. 10 in control group) with motor complete SCI involving C8-T10 and AIS A or B classification, will be recruited to participate in a 9 months trial. The primary goal of this work is to ensure that our procedures are safe and effective for persons with motor complete SCI.

The following timeline will be implemented to meet our recruitment goals. We plan to recruit 20 Veterans/non-Veterans over a 2-year period (24 months). We plan to start participants enrollment in the 1st quarter of year-1 and finish in 1st quarter of year-2 (see recruitment table below). We will continue to collect data and finish analysis by the 4th quarter of year two. This is feasible considering our previous experience recruiting for the parent study. Also, we do not anticipate attrition due to prior established compliance with telehealth home-based study. We plan to offer resistant training to participants on a flexible schedule so as to accommodate their lifestyle, to avoid attrition. Participants will be randomized to either intervention or control group.

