## **Risk to Subjects.**

Every effort will be made to minimize potential harm to individuals during the study. There will strict adherence to the protocol's inclusion/exclusion criteria. However, the following may pose potential risk to study participants:

Potential source of risk	Potential Risk	Possibility of occurring
Pressure to skin from weights or skin irritation from weights or during exercise	Pressure injury (break to skin)	Occasionally but no more than usual from daily activities
DXA/MRI	No significant risk This research study will involve exposure to radiation from 2 whole body DEXA scans and MRI with no contrast. This radiation exposure is not necessary for medical care and is for research purposes only. All radiation exposure increases the risk of developing cancer in the future. The total amount of radiation that would be used in this study is equal to less than one day of exposure from natural background radiation. Permission would be obtained from the CVVHCS Radiation Safety Committee, who will review the use of radiation in this research study, involving minimal risk and necessary to obtain the desired research information. Participants will be instructed to tell their Providers if they have participated in other research studies or received any other medical care involving radiation in the recent past.	Unlikely
Phlebotomy	Phlebotomy can cause pain, bruising at the site of the venipuncture, nerve damage, hematoma or infection	Rare
Electrical stimulator/weights (Risk of fracture)	SCI is commonly associated with bone weakness and weight bearing on the participant's limbs while exercising on the rowing machine may increase risk of fracture to already weakened bones.	Rare

Autonomic Dysreflexia (AD)	Weights and exercise to limbs of participants may pose as noxious stimuli that may lead to symptoms of AD (headache, pounding in the head, ringing in the ears, dizziness, blurry vision, sweating, anxiety, flushing, tightness in the chest, stuffy nose, heart flutters, or difficulty breathing), especially in those with cervical level of injury and high thoracic level of injury (T6 and above).	Rare
Falls	Falls could occur during training or transfer unto testing equipment (MRI/DXA table or in the home during transfer to/from wheelchair unto rowing machine.	Rare
Risk of Fracture	SCI is commonly accompanied by bone weakness and weight bearing on the participants' limbs may increase their risk of sustaining stress/low impact mechanical fracture.	

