**Adverse Events:**

All participants will be monitored for any changes in health status from baseline. The SCI Provider on record for each participant will be notified of any changes that may require attention. An adverse event is any experience that has taken place during research project, which, in the opinion of the investigators, was harmful to the research participant, increased the risks of harm in the research, or had an unfavorable impact on

the risk/benefit ratio. Adverse events will be monitored throughout the study period via physical examinations, vital signs, laboratory tests, review of medical charts, and verbalized concerns by the participants, caregivers, significant other or family member. Any adverse event will be documented in each participant's file. Files will be reviewed for adverse events, protocol violations, and reasons for dropouts/withdrawals every ten days. The PI will provide CVVHCS IRB an annual summary of adverse events. All serious adverse events (SAEs), such as those that are life-threatening or involve hospitalization, will be promptly reported to CVVHC IRB Research Subjects Protection Program. Serious adverse event is defined as the unexpected medical occurrence associated with the research procedure that may lead to death, life-threatening medical condition, inpatient hospitalization for or longer than 24 hours, persistent or significant incapacity or substantial disruption of the ability to engage in normal activities of daily living.

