### **Data and Safety Monitoring Plan.**

The PI will monitor and review the protocol as well as data collection every month to evaluate participants' safety, data quality, and study progression and execution. The PI will review the protocol for any major concerns prior to implementation. The local data monitoring board will meet every 6 months to review/discuss the study. The data monitoring board will have the option to request stopping or cessation of participants' enrollment and all research procedure, if deemed necessary. It is unlikely that they would find significant improvement in collected bone parameters at mid-intervention (4.5 months) in the intervention group because bone requires a longer time for adaptation, especially in persons with SCI. However, should there be significant improvement (s) in the intervention group compared to the control group, the data monitoring team could terminate the study early. The PI will also assess the performance of overall study operations and any other relevant issues, as necessary. The Data and Safety Monitoring Board (DSMB) is responsible for overseeing the safety of the research and report observations/findings to the IRB on an annual basis. The data monitoring team will review all unanticipated problems involving risks to subjects or others associated with the protocol and provide an independent report of the event to the IRB. They may discuss the research protocol with the investigators; shall have authority to stop a research protocol in progress, remove individual human subjects from a research protocol, and take whatever steps necessary to protect the safety and well-being of human participants until the IRB can assess the monitor's report; and shall have the responsibility to promptly report their observations and findings to the IRB. A letter will be drafted from the DSMB and will be attached with the annual summary report to the IRB. Elements in the letter will include the followings:

- Evidence of study-related AEs

- Evidence of efficacy according to pre-established statistical guidelines, if appropriate;
- Data quality, completeness, and timeliness
- Performance of the specific research center
- Adequacy of compliance with goals for recruitment and retention
- Adherence to the protocol
- Factors that might affect the study outcome or compromise the confidentiality of the trial data (such as protocol violations)

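### The definition of a serious adverse event adds unexpectedness and relatedness, in conflict with the prompt-reporting sentence just before it

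*Combined protocol and SAP*

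**What the plan says.** Two adjacent sentences in the protocol's Adverse Events section bear on the point. The first is the reporting rule: "All serious adverse events (SAEs), such as those that are life-threatening or involve hospitalization, will be promptly reported" to the IRB. The second is the definition: "Serious adverse event is defined as the unexpected medical occurrence associated with the research procedure" that may lead to death, a life-threatening condition, "inpatient hospitalization for or longer than 24 hours", lasting incapacity, or substantial disruption of daily activities. Nothing in the protocol defines *unexpected*, and no other section gives a different definition of a serious adverse event.

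Adverse events that are not serious go into the participant's file, and "The PI will provide CVVHCS IRB an annual summary of adverse events".

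The risk table under Risk to Subjects names fracture ("weight bearing on the participant's limbs while exercising on the rowing machine may increase risk of fracture to already weakened bones") and autonomic dysreflexia ("Weights and exercise to limbs of participants may pose as noxious stimuli that may lead to symptoms of AD"). Both are rated rare there, although a second fracture row carries no rating.

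Two other sections depend on related terms. The last study removal criterion applies to a serious adverse event that the SCI physician judges to require withdrawal. In the Data and Safety Monitoring Plan the board is to "review all unanticipated problems involving risks to subjects or others associated with the protocol" and to send the IRB an independent report on them.

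**The concern.** Seriousness is a statement about outcome. Whether an event was foreseen and whether the study caused it are separate judgements, usually made afterwards and open to revision. Here all three are conditions for the same label, and prompt IRB reporting depends on that label.

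The events most likely to fail the expectedness condition are those the protocol itself foresees. The relatedness condition makes classification depend on a causal judgement, in a trial where the PI supervises the resistance training by telehealth and the two interventions are visibly different. The recruitment section says "The primary goal of this work is to ensure that our procedures are safe and effective", so the reporting rule for serious harm should not be open to two readings.

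**Working it through.** No formula applies, and the plan states no figure to reproduce. The check applies each sentence, as written, to the same events. Suppose each event leads to an admission of at least 24 hours, and take *unexpected* to mean not among the risks the protocol lists. That meaning is an assumption.

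| Event | Listed outcome | Unexpected | Associated | Under the definition | Under the reporting sentence |
|---|---|---|---|---|---|
| Fracture during training | yes | no (listed risk) | yes | not serious | serious, prompt report |
| Autonomic dysreflexia during training | yes | no (listed risk) | yes | not serious | serious, prompt report |
| Unforeseen illness judged unrelated | yes | yes | no | not serious | serious, prompt report |
| Unforeseen event judged related | yes | yes | yes | serious | serious, prompt report |

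The sentences agree only in the last row. They also differ on length of stay: the definition sets 24 hours, while the reporting sentence mentions hospitalisation without a minimum.

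Next, follow an event from one of the first three rows if staff apply the definition.

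1. **IRB.** Prompt reporting is promised only for serious events, so the stated fallback is the yearly summary.
2. **Monitoring board.** Its independent event report covers unanticipated problems, which again depends on expectedness. Its letter to the IRB, however, covers study-related adverse events with no such condition, and it must promptly report its own findings.
3. **Withdrawal.** The criterion tied to the serious-event label would not apply. Other removal criteria, including hospitalisation for an acute medical problem and hypercalcemia, do not use the label and could still apply.
4. **Detection.** The event is still documented. Files are reviewed every ten days, the PI reviews safety monthly, and the board meets every six months.

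So the literal reading delays notice to the IRB and changes the event's classification. It does not make the event disappear.

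**The case against.** The strongest reply is that the exclusion is inferred. *Unexpected* is undefined, and a risk rated rare can fairly be called unexpected in a given participant. On that reading a hospitalised fracture or dysreflexia episode would still qualify. The reporting sentence points the same way, since a hospitalised fracture fits its examples as they stand. This reply stands in part: it shows that the text is ambiguous, not that it is sound. It also does not reach the third row of the table, where the relatedness condition alone excludes the event.

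A reader might infer that the reporting sentence simply takes over the narrow definition, so that hospitalised fractures are certain to be withheld from prompt reporting. The documents do not support that. The examples carry no conditions, so what they show is a conflict between two sentences.

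A reader might also infer that serious events would be undercounted, and more so in the stimulation and rowing arm. With 10 per arm, one omitted participant is 1/10 = 10 percentage points, but that holds for any single event in any arm of ten and estimates nothing. The Data Analysis Plan contains no serious-event count by arm that could be biased, and because adverse events are documented, such a count could be rebuilt by outcome. The argument for a difference between arms is also mixed. Both arms take vitamin D and both transfer to the MRI and DXA tables, while the protocol describes pressure injury as no more frequent than in daily life.

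**Conclusion.** The definition conflicts with the sentence before it and, read literally, can leave foreseen or unrelated serious events out of prompt IRB reporting and out of one withdrawal criterion. This is a should-fix matter. The size is a possible delay in IRB notice, up to about a year if the annual summary were the only route, and inconsistent labelling. The ten-day, monthly and six-monthly reviews limit the consequence. No numerical bias is shown, and no planned efficacy analysis is affected.

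For fracture and dysreflexia the conclusion assumes that a listed risk counts as expected, which is the natural reading but is not stated. For events judged unrelated it needs no such assumption.

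**What to change.** Reconcile the two sentences. Define a serious adverse event only by the outcomes already listed in the Adverse Events section, regardless of expectedness or cause, and use the same hospitalisation wording in both sentences. Record expectedness and relatedness as separate judgements for each event. Report serious events by arm on the outcome-based definition. Check that the withdrawal criterion and the board's event review still read as intended once the label is wider.

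The cost is a reworded definition, two recorded items per event, and somewhat more prompt reports to the IRB, including admissions unrelated to the study. Routine admissions are common in this service: in the protocol's fiscal 2019 table, annual evaluation and respite care make up about 368 + 154 = 522 of the 87 + 368 + 269 + 154 = 878 listed, or 522/878 = 59%. Those figures describe the whole inpatient service, not trial participants. The extra load can be limited by stating that pre-planned admissions, such as annual evaluation or respite care, do not count as serious events.

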### **Subject's burden:**

The current study **was designed to reduce and minimize participants' burden** including transportation and participation time. Although participation may impose a significant burden, every effort will be taken by the study team to reduce the stressors and burden associated with study participation over the study period. Each intervention session would last approximately 60 minutes. The current study is designed to allow participants to participate from the comfort of their homes using video telehealth technologies. This should provide some level of control over most SCI factors that may otherwise impact the outcome of the study, for example, stress associated with travel burden that could lead to attrition. Each participant will have the liberty to miss up to

15% of scheduled Telehealth visit, due to unanticipated events, such as, short duration of acute illness, medical appointments, or vacation, without being asked to withdraw or disenrolled from the study. We believe that we can retain participants through the duration of the study (9 months) by:

- a) Providing free transportation for tests at the medical center (most Veterans already have this benefit).
- b) Providing flexible hours to accommodate education and work-related schedules.
- c) During data collection, we will provide sufficient time for participants to have their meals and use medications.
- d) Using a comprehensive team approach that would allow participants to engage in recreational activities and avail themselves of Psychology (if desired) and Nutritional services.

**Benefits:**

**Potential benefits of research to Veterans and others:**

The proposed study is geared towards improving both bone and muscle strengths and will benefit the participants in increasing muscle blood flow, blood glucose uptake as well as decrease bone demineralization. The anticipated benefits of the current trial should be viewed in the light that the proposed work will serve as a pilot work for future protocols by providing supporting preliminary data to adequately power future clinical trials.

We hope findings from this work will provide supporting evidence to establish the resources necessary to **accelerate research and development of therapies for bone loss**

**attenuation and improved functionality and quality of life for persons with chronic SCI.** It is anticipated that this will reduce the costs associated with managing low impact fractures secondary to bone loss after SCI. The PI will make every effort to disseminate the knowledge gained from this trial through presentations at local, national and/or international scientific meetings. And also, by manuscript preparations and submission to high impact peer-reviewed journals for publications. The intervention in this study may directly benefit participants physiologically, aside from the financial compensation, by increasing muscle mass and improving blood flow. However, if there are no direct benefits to participants, the information gained, has the potential to help others in the future.

**Importance of Knowledge to be gained**

The prevalence of individuals with SCI has been estimated to be 250,000-400,000 with an estimated 18% growth in the prevalence since 1988. Of the more than 46,000 Veterans with SCI-related disability, more than 50% will develop osteoporosis in the first year of injury if the process is not mitigated. The incidence of osteoporosis in this population gets even higher and exceeds 80% with increased years since injury and predisposes persons with SCI to low impact mechanical fractures. In fact, 50% of

individuals with SCI will sustain low impact mechanical fractures during their lifetime. It is worrisome that the cost of managing osteoporosis-related fractures may cost about \$25 billion by 2025. Fortunately, mechanical loading of paralyzed limbs has been shown to attenuate bone loss providing hopes for mitigation of bone loss after SCI, thereby slowing down progression to osteoporosis and associated complications. In addition, electrical stimulation has been shown to partly reduce the loss of bone mineral density in the femur when treatment was initiated early post SCI. Therefore, this study proposes to combine loading and electrical stimulation in addition to vitamin D supplementation, in an attempt to attenuate bone loss in persons with SCI. Considering the time, cost and potential associated-risks, we are proposing the use of both electrical stimulation and paralyzed limb loading strategy plus vitamin D supplementation to achieve bone attenuation. Assuming that our protocol is successful in attenuating bone loss, many of the 46,000 Veterans with SCI stand to benefit as does VHA in health care costs savings.

**Clinical Trial Requirements:** This is a drug trial and registration with Clinical Trials is mandated. We are aware of this requirement and are experienced in complying with all regulatory requirements.

### **Data and Safety Monitoring Plan.**

The PI will monitor and review the protocol as well as data collection every month to evaluate participants' safety, data quality, and study progression and execution. The PI will review the protocol for any major concerns prior to implementation. The local data monitoring board will meet every 6 months to review/discuss the study. The data monitoring board will have the option to request stopping or cessation of participants' enrollment and all research procedure, if deemed necessary. It is unlikely that they would find significant improvement in collected bone parameters at mid-intervention (4.5 months) in the intervention group because bone requires a longer time for adaptation, especially in persons with SCI. However, should there be significant improvement (s) in the intervention group compared to the control group, the data monitoring team could terminate the study early. The PI will also assess the performance of overall study operations and any other relevant issues, as necessary. The Data and Safety Monitoring Board (DSMB) is responsible for overseeing the safety of the research and report observations/findings to the IRB on an annual basis. The data monitoring team will review all unanticipated problems involving risks to subjects or others associated with the protocol and provide an independent report of the event to the IRB. They may discuss the research protocol with the investigators; shall have authority to stop a research protocol in progress, remove individual human subjects from a research protocol, and take whatever steps necessary to protect the safety and well-being of human participants until the IRB can assess the monitor's report; and shall have the responsibility to promptly report their observations and findings to the IRB. A letter will be drafted from the DSMB and will be attached with the annual summary report to the IRB. Elements in the letter will include the followings:

- Evidence of study-related AEs

- Evidence of efficacy according to pre-established statistical guidelines, if appropriate;
- Data quality, completeness, and timeliness
- Performance of the specific research center
- Adequacy of compliance with goals for recruitment and retention
- Adherence to the protocol
- Factors that might affect the study outcome or compromise the confidentiality of the trial data (such as protocol violations)

